1.0 STUDY SYNOPSIS

This study involves administration of an integrated radiotherapy boost to cancerous unresected pelvic and para-aortic nodal disease from gynecologic cancers. Many studies have utilized a sequential boost to deliver a total dose of 55 – 60 Gy to the pelvic sidewall (covering the lower pelvic lymph nodes), including 8-10 Gy that is usually delivered with brachytherapy [3,9,32]. This study treatment plan will escalate the dose to pelvic and para-aortic nodal disease from 60 Gy in 2.4 Gy per fraction to 70Gy in 2.8 Gy per fraction in 3 dose cohorts, using an integrated boost technique utilizing the same number of fractions for all cohorts (25 fractions) while the elective volumes are held constant at 45Gy . The cervix and uterus will be preferentially boosted with brachytherapy if clinically indicated.

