4.3 Rationale for Dose Intensification in Vulvar Cancer

The primary treatment for stage IB-IV vulvar cancer is surgery followed by adjuvant radiation with or without chemotherapy for risk factors including nodal involvement and close or positive margins [11]. For locally-advanced vulvar cancers with or without unresectable nodal disease, neoadjuvant chemoradiation to 46 Gy renders 70-80% of patients eligible for conservative pelvic surgery and has a 30-

50% pathologic complete response rate [2,4,19,20]. In these studies, many patients who achieve pathologic complete response have durable local control. Given these positive results, it may be possible to improve response rates and loco-regional control with radiation dose escalation. However, significant toxicity is associated with neoadjuvant CRT: acute grade 3-4 cutaneous toxicity in 50-60% of patients and surgical wound complications in 20-30% [19,20]. In two series representing 110 patients, 3 patients died from treatment complications including femoral artery necrosis, leukopenia and sepsis, and wound infection and sepsis [19,20]. It may be possible to reduce this complication rates using IMRT technique. At the University of Pittsburgh, 18 patients with locally-advanced vulvar cancer were treated with neoadjuvant IMRT to 46 Gy with concurrent chemotherapy [2]. Among these patients, 30% experienced surgical wound complications that healed 3-6 months postoperatively.

This protocol will include the subset of locally advanced vulvar cancer with gross residual or unresected disease within the pelvis, for those patients whom treatment intensification may hold some benefit.

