9.0 EVALUATIONS DURING AND AFTER TREATMENT

9.1 Overall Schema

Patients will undergo CT scans prior to treatment as part of the standard staging procedure for gynecologic cancers. Some patients may also undergo PET and/or MRI scans at the discretion of the attending radiation and gynecologic oncologists. Patients will be assessed on a weekly basis, or more frequently as indicated, during the course of therapy by the attending radiation oncologist. During this visit, an interim history and directed physical examination will be performed and treatment-related

toxicity will be prospectively recorded using CTCAE version 4.0. A CBC will be obtained weekly during treatment. Other laboratory work will be obtained as deemed necessary. Cone Beam CT (CBCT) scans will be obtained weekly for the first 2 weeks and then at the discretion of the attending radiation oncologist. Patients will then be evaluated by either gynecologic oncology or radiation oncology every 3 months for follow-up. Assessment for late toxicity at 3-4 months after treatment, and will continue at 6 month interval for 2 years following treatment.

	Pre Treatment	Week 1	Week 2	Week 3	Week 4	Week 5	Follow-up¹
CBC	X	X	X	X	X	X	
Toxicity assessment		X	X	X	X	X	X
CBCT³		X	X	X ²	X ²	X ²	
PET-CT (optional) MRI (optional) for planning	X						

1. Follow-up post radiotherapy for radiation oncology at 4-6 weeks, and every 6 months for 2 years with interval gynecology oncology follow-up (+/- 3 month)
2. Optional
3. Cone beam CT

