9.2 Criteria for Going Off Protocol

- 9.2.1. Development of local, regional, or distant progression during treatment.
- 9.2.2. Intolerable side effects from therapy despite in spite of measures to ameliorate them.
- 9.2.3. Noncompliance with protocol requirements.
- 9.2.4. Patient refusal or withdrawal of consent.
- 9.2.5. Discretion of PI or treating physician.

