11.0 STATISTICAL CONSIDERATIONS

The maximum sample size of this study is 24 (6 patients at each of the 4 dose cohorts). The accrual rate is estimated to be about 4 patients per year. The dose-limiting toxicities are defined in Section 9.1.6 The dose cohorts and the dose escalation rules are defined in Section 9.1.5 and 9.1.7 respectively. These sections show that there are separate and independent dose escalation rules for early DLT's (toxicities that occur in the first 4 weeks of treatment) and late DLT's (toxicities that occur after 4 weeks). Likewise, there are separate definitions of dose-limiting toxicity for early and late toxicities. Thus, the trial could de-escalate due to either early or late toxicities. Because of the independence of the two sets of rules, a dose cohort of 6 patients in which one patient has an early DLT and one patient has a late DLT would not result in de-escalation of the dose. If a patient has both an early and a late DLT, the dose escalation rules would treat these DLT's as if they happened to two different patients.

Toxicities will be tabulated within each dose cohort by type, grade, and whether they were early or late. All toxicities will also be evaluated for their relationship to treatment and whether they were expected or unexpected. Time to local-regional recurrence (TTLR), time to distant recurrence (TTDR), disease-free survival (DFS), and overall survival (OS) will be estimate in all patients using the Kaplan-Meier method. TTLR will be defined as the time from first radiation treatment to local or regional (nodes) recurrence, whichever comes first, ignoring distant failures and censoring deaths. TTDR will be defined as the time from first radiation treatment to distant recurrence, ignoring local and regional failures and censoring deaths. DFS will be defined as the time from first radiation treatment to any recurrence (local, regional, or distant) or death, whichever comes first. OS will be defined as the time from first radiation treatment to death due to any cause.

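### The TTLR event is recurrence only, so nodal disease that never clears or that progresses on treatment is not counted, which biases local-regional control upward

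*Combined protocol and SAP*

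**What the plan says.** Section 11.0 gives the definition: "TTLR will be defined as the time from first radiation treatment to local or regional (nodes) recurrence, whichever comes first", followed by "ignoring distant failures and censoring deaths". For DFS it says "DFS will be defined as the time from first radiation treatment to any recurrence (local, regional, or distant) or death, whichever comes first". These endpoints, with TTDR and OS, "will be estimate in all patients using the Kaplan-Meier method". They serve secondary objective 3.2.1 (rates of local-regional control, DFS and OS).

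The synopsis (Section 1.0) describes the target as "cancerous unresected pelvic and para-aortic nodal disease from gynecologic cancers", and Section 8.1.3 builds the boost volume from the gross nodal volume.

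Progression appears as an outcome in one place only, the first off-protocol criterion in Section 9.2: "Development of local, regional, or distant progression during treatment". That criterion is not linked to any endpoint. For follow-up, footnote 1 of the Section 9.1 table gives "Follow-up post radiotherapy for radiation oncology at 4-6 weeks, and every 6 months for 2 years". The follow-up column is marked for toxicity only, and no follow-up imaging or disease-status assessment is listed. Recurrence is not defined anywhere, and no rule or date is given for disease that does not clear.

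**The concern.** A recurrence presupposes a period without disease. Most of these patients have gross nodal disease at the first fraction, so a node can fail in two ways that are not recurrences in the plain sense: it never clears, or it grows during the 25 fractions. Those are the failures that a nodal boost is meant to prevent.

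In TTLR the omission is permanent, because a patient who dies with uncontrolled nodes is censored at death. The resulting rate would naturally be set beside the 50-80% local-regional control figures in Table 1 of Section 4.2. That same section criticises an earlier trial whose failure scoring could not show whether the nodal dose was adequate. An endpoint that leaves out persistence has a similar weakness.

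**Working it through.** **Design figure.** Section 11.0 gives a maximum of 24 patients: 6 per cohort × 4 cohorts = 24, which reproduces. No target rate, test or power is stated for TTLR or DFS, so the check concerns the event definition.

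**How each course is scored under the wording of Section 11.0**

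| Course | TTLR | DFS |
|---|---|---|
| Clears, then recurs locally | Event | Event |
| Never clears, dies | Censored at death | Event at death, or at an earlier recurrence elsewhere |
| Never clears, alive at last follow-up | Censored | Censored unless it recurs elsewhere |
| Progresses on treatment, off protocol (9.2.1) | No event | Event only at a later recurrence or death |

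**Size for TTLR.** Inputs:
- F, the total local-regional failure: 30-50% at 3 years in the prospective trials discussed in Section 4.2, and about 40-50% local failure in Section 10.0. I take F to include persistence and progression.
- f, the share of F that is persistence or progression: not in the documents. Assumed 10%, 25% and 50%.

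Control with these counted as events = 1 − F.

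Control as written:
- if such patients stay at risk without an event: 1 − F(1 − f), an overstatement of F·f;
- if they are censored early: 1 − F(1 − f)/(1 − F·f), a smaller overstatement.

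Worked case, F = 40% and f = 25%: counted, 1 − 0.40 = 60%. As written, 1 − 0.40 × 0.75 = 70%, or 1 − 0.30/0.90 = 66.7%.

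| F | Counted | As written, f = 10% | f = 25% | f = 50% |
|---|---|---|---|---|
| 30% | 70% | 72.2-73% | 75.7-77.5% | 82.4-85% |
| 40% | 60% | 62.5-64% | 66.7-70% | 75-80% |
| 50% | 50% | 52.6-55% | 57.1-62.5% | 66.7-75% |

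The overstatement runs from 2.2 points (F = 30%, f = 10%, censored early) to 25 points (F = 50%, f = 50%, at risk). The patients affected number 24·F·f, from 0.7 to 6.0 of 24.

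**Kaplan-Meier illustration (hypothetical).** Take 24 patients: 4 with persistent disease found at 4 months who die at 12 months; 6 who recur at 9, 11, 14, 16, 20 and 22 months; 14 event-free past 24 months.

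- TTLR at 24 months, persistence counted: 14/24 = 58.3%.
- TTLR at 24 months, as written: two events while 24 are at risk give 22/24. The four are censored at 12 months, leaving 18, and four more events give 14/18. The product is 22/24 × 14/18 = 71.3%, so the difference is 13.0 points.
- DFS at 6 months: 20/24 = 83.3% counted, against 100% as written. At 12 months both give 18/24 = 75.0%, and at 24 months both give 14/24 = 58.3%, because the deaths have by then entered as events.

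**The case against.** The strongest reply is that investigators would score a node that never clears as a failure anyway. Section 11.0 does use the word failures beside recurrence, and objective 3.2.1 speaks of control. If persistence were scored that way, the bias would disappear. But the text uses failures only for outcomes to be ignored and never says that the word covers persistence or progression. It also gives no date for such an event. The rule as written is recurrence, and an unwritten practice would leave the scoring to case-by-case choice.

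Three other points stand as limits. Eligibility (Section 6.1) accepts nodes positive by pathology, so some patients may have had nodes resected, and for them recurrence is a suitable term. The endpoints are secondary and descriptive, with no decision attached. And f is assumed.

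A reader might go further in three ways that the documents do not support:
- *That residual disease is common here, from the 30-50% pathologic complete response in Section 4.3.* That figure follows preoperative treatment to 46 Gy in vulvar cancer. It does not measure nodal persistence after a 60-70 Gy nodal boost. The nearest nodal figure, from a retrospective series in Section 4.2, is 4% pelvic nodal failure at 2 years with mean nodal doses of 67-74 Gy. At F = 4% the overstatement of nodal control could not exceed 4 points, even with f = 100%.
- *That DFS also omits these patients.* DFS counts death, so the event is usually delayed and is missed only in survivors without a later recurrence.
- *That each uncounted patient adds 1/24 = 4.2 points.* This is a crude proportion. In the illustration four patients shift the planned Kaplan-Meier estimate by 13.0 points, not 4/24 = 16.7.

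**Conclusion.** The point holds for TTLR. As written, persistent and progressing local or nodal disease is never an event, and nothing elsewhere in the protocol makes it one. The direction of the bias is upward whenever such a patient exists. Its size cannot be taken from the documents: about 2 to 25 points if 10-50% of a 30-50% local-regional failure rate is of this kind, and less if failure is rarer. For DFS the effect is smaller and mainly early. MTD, the escalation rules and the sample size do not depend on these definitions. The correction is worth making because local-regional control is a stated objective.

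**What to change.** In Section 11.0:
- Define the local-regional event as the first of progression during or after treatment, persistent local or nodal disease at a stated post-treatment assessment, or recurrence.
- Use progression or recurrence as the event wording for TTDR. For DFS, count the local-regional event above, distant progression or recurrence, or death.
- Count progression that takes a patient off protocol under 9.2.1 as an event on the date of progression.
- State the criterion for calling disease persistent and the date assigned to that event.

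In Section 9.1, record disease status (none, persistent, progressed or recurred, with date and method) at the existing follow-up visits, from whatever examination or imaging is done as routine care. The assessment needs to be named explicitly. Section 9.1 mentions 3-4 months only for late toxicity, the table footnote gives 4-6 weeks and then every 6 months, and neither lists imaging.

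The cost is a few sentences, one added data field, and agreement on the criterion for persistence. TTLR and early DFS figures will look less favourable. Treatment, dose and enrolment do not change.

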3.2 Secondary Objectives

3.2.1 To determine local-regional control, disease free survival, and overall survival rates with integrated boost radiation therapy.

3.2.2 To prospectively gather acute and late toxicity data.

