There is some data suggesting benefit to increasing the dose to involved nodes. A retrospective study of 200 patients at Washington University excellent lymph node control rates were reported with chemoradiation [10]. The mean dose to positive pelvic lymph nodes ranged from 67 to 74 Gy and the 2 year pelvic lymph node and cervix failure rates were 4% and 12% respectively. Two prospective studies, GOG 125 and RTOG 92-10, evaluated the use of a pelvic sidewall boost along with extended-field chemoradiation in patients with pathologically positive para-aortic lymph nodes (table 1) [9,32]. In RTOG 92-10, patients were treated with accelerated, hyperfractionated radiation and involved para-aortic lymph nodes were also boosted to total doses of 54-58Gy. Both studies showed that 30 to 40% of patients with pathologically proven positive para-aortic nodes were free of disease at 3 years. Overall, there was higher incidence of local-regional failures (30-50% at 3 years) compared to the Washington University or University of Pittsburgh series. The higher likelihood of failure, is probably related to the fact that patients had more advanced disease and were followed prospectively. Although in GOG 125 20% of patients had isolated pelvic failures but, central versus nodal recurrences were not scored separately, and so it is unknown if radiation doses were adequate to control nodal disease.

Thus, patients with residual or unresectable nodal disease have significantly worse outcomes in cervical cancer. Prospective studies using IMRT in the definitive treatment of cervical cancer are needed to correlate treatment volumes and radiation dose with pelvic and para-aortic disease control rates This study will accrue this subset of patients who have the most to gain from treatment intensification.

Table 1 Outcomes with concurrent EFRT and chemotherapy

Study	Study type n	Radiation	Chemo	Parametrial / PA nodal boost	LRC (yr f/u)	OS (yr f/u)	Acute GI	Late GI (yr f/u)
GOG 125 [32]	Phase II 95	Conventional WP + PA	Cisplatin 5-FU	Yes/No	(3) 70%	(3): 39%	G 3-4: 19%	G 3-4 (4) 14%
RTOG 92-10 [9]	Phase II 30	Conventional WP + PA RT BID	Cisplatin 5-FU	Yes/Yes	(3): 50%	(4): 29%	G 3-4: 50%	G 3-4 (3): 34%
Beriwal [3]	Retrospective 36	IMRT WP + PA	Cisplatin	Yes/Yes	(2): 80%	(2): 65%	G 3-4: 3%	G 3-4 (2): 10%

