8.1.7 Dose Escalation Schema

Dose escalation will operate in the following fashion based on acute DLTs:

1. 3 patients will be accrued to dose level X (starting at level 1)
2. If there are any acute DLTs noted in these initial three participants, and additional three will be accrued (for a total of six).
3. If there is a second acute DLT, accrual will be halted for that cohort, and the dose will be deescalated to level X-1.
4. If 0/3 or 1/6 participants have an acute DLT, after a minimum follow up of 6 weeks, accrual to cohort X+1 may begin.
5. The candidate cohort for MTD will accrue a total of 6 patients. Thus if the dose deescalates, the dose cohort X-1 must have 6 participants before declaration of MTD. Similarly if the protocol proceeds to level 3, then it will accrue 6 participants even if no patient has an acute DLT.

The following schema will be used for late DLTs in conjunction with the above acute rules:

1. Patients will be monitored for late toxicity at every follow-up for 3 years.
2. If a late DLT observed in cohort Y, accrual in that and any higher cohort will be held until there is a minimum of 3 month follow up for all patients.
3. If a second late DLT is observed in cohort Y, then the dose will be de-escalated to Y-1 as per the above schema.
4. If there are no additional late DLTs in cohort Y, then a total of 6 patients must accrue to cohort Y, with a minimum of 3 months follow-up with no further late DLTs before the dose may be escalated to, or for accrual to resume in cohort Y+1.

Of note, acute and late DLTs will be counted separately. Thus if a patient has both an acute DLT and a late DLT, they will be counted as 1 DLT for both schema. If a patient has an acute DLT but not a late DLT, they will only be counted in the acute schema. The only exception will be a patient has an acute

DLT which does not resolve to less than grade 2 by 3 months: these will be counted as both acute and late toxicity for determination of MTD.

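### Censoring deaths in the Kaplan-Meier estimates of local-regional and distant recurrence overstates recurrence when deaths without recurrence come first; Table 1 implies such deaths are common

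*Combined protocol and SAP*

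**What the plan says.** Section 3.2 sets the secondary objective: "To determine local-regional control, disease free survival, and overall survival rates with integrated boost radiation therapy". Section 11.0 serves it with four time-to-event endpoints that "will be estimate in all patients using the Kaplan-Meier method". TTLR runs from first radiation treatment to "local or regional (nodes) recurrence, whichever comes first, ignoring distant failures and censoring deaths". TTDR runs to "distant recurrence, ignoring local and regional failures and censoring deaths". DFS counts any recurrence or death, and OS counts any death. The document plans no cumulative-incidence or other competing-risk estimate. It also does not say that the recurrence endpoints are meant as net quantities, that is, recurrence in a hypothetical setting without death.

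**The concern.** Kaplan-Meier censoring assumes that a censored patient keeps the same future risk as those still under observation. A patient who has died without local-regional recurrence has no such risk. Censoring her passes her remaining risk to the survivors, and 1-KM then rises above the proportion of patients who recur. More patients would not remove this excess, and a confidence interval does not show it. TTLR also ignores distant failure, so a patient who dies of distant disease is simply censored for local-regional recurrence.

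At stake is the local-regional control rate promised in Section 3.2, which would be understated. The problem matters only if deaths without recurrence are frequent and come before some of the recurrences. The protocol's own background table allows a check on the first condition.

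**Working it through.** **Inputs.** Section 4.2 ("Table 1 Outcomes with concurrent EFRT and chemotherapy") gives local-regional control (LRC) and overall survival (OS) at the same time point for two series:
- GOG 125, 3 years: LRC 70%, OS 39%.
- Pittsburgh IMRT series, 2 years: LRC 80%, OS 65%.

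The RTOG 92-10 row is left out because its LRC is at 3 years and its OS at 4 years. Section 11.0 states no recurrence rate or precision for TTLR or TTDR, so there is no such figure to reproduce. Its maximum sample size is 6 × 4 = 24. If no DLT occurs, 3 + 3 + 6 = 12 patients are treated, because Section 8.1.7 says: "Similarly if the protocol proceeds to level 3, then it will accrue 6 participants even if no patient has an acute DLT".

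**Step 1: deaths without local-regional failure.** The smallest possible share arises if every patient with failure has also died: (1 − OS) − (1 − LRC).
- GOG 125: 61% − 30% = 31%.
- IMRT series: 35% − 20% = 15%.

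**Step 2: excess under constant hazards.** Let c1 be the cumulative incidence of local-regional failure and c2 that of death without it. Then H = −ln(1 − c1 − c2) and 1-KM = 1 − exp[−H·c1/(c1 + c2)].
- GOG 125 at 3 years (0.30, 0.31): H = −ln 0.39 = 0.9416. Multiplying by 0.30/0.61 gives 0.4631, so 1-KM = 37.1% against 30.0%, **+7.1 points**.
- GOG 125 at 2 years: H = 0.9416 × 2/3 = 0.6277. Cumulative incidence is (1 − e^−0.6277) × 0.30/0.61 = 22.9%, and 1-KM = 26.6%, **+3.6 points** before rounding. Two years is the scheduled clinic follow-up in Section 9.1 ("every 6 months for 2 years with interval gynecology oncology follow-up"). Section 8.1.7 monitors late toxicity for 3 years.
- IMRT series at 2 years (0.20, 0.15): H = −ln 0.65 = 0.4308. Multiplying by 0.20/0.35 gives 0.2462, so 1-KM = 21.8% against 20.0%, **+1.8 points**.

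**Step 3: other assumptions.** Table 1 gives no event timing, so the size was varied.

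| Assumption | GOG 125, 3 years | IMRT series, 2 years |
|---|---|---|
| All failures in the first 6 months, constant death hazard | +1.3 | +0.5 |
| All failures in the first 12 months, constant death hazard | +2.6 | +1.0 |
| Constant hazards, minimum competing deaths | +7.1 | +1.8 |
| Constant hazards, a quarter of failed patients alive (c2 = 0.385; 0.20) | +9.7 | +2.5 |
| Any timing, minimum competing deaths: from c1 to c1/(1 − c2) | 0 to +13.5 | 0 to +3.5 |

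The upper limits in the last row are 0.30/0.69 = 43.5% and 0.20/0.85 = 23.5%. In the early-failure rows, a failure hazard λ acts only up to time τ and a constant death hazard μ acts throughout. Both are solved to match c1 and c2, and 1-KM = 1 − exp(−λτ).

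If the Table 1 control rates are themselves death-censored Kaplan-Meier figures, and all failed patients have died, constant hazards give a cumulative incidence of 23.1% against 30% (+6.9) and 18.1% against 20% (+1.9).

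**Step 4: sampling error.** Simulation used 20,000 trials per setting, constant hazards and complete follow-up. The SD of 1-KM at n = 24 was 11.3 points (GOG 125 rates, 3 years), 9.9 (same rates, 2 years) and 8.9 (IMRT series rates, 2 years). At n = 12 the corresponding values were 16.2, 14.0 and 12.5 points. At n = 24, mean 1-KM was 37.1%, 26.6% and 21.8%; the Aalen-Johansen means were 30.0%, 23.0% and 19.9%.

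**TTDR.** Table 1 has no distant-failure data. The direction follows from the method, but the size cannot be derived.

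**The case against.** **The estimand may be deliberate.** Section 11.0 states its censoring rule openly. Under independent censoring, death-censored Kaplan-Meier estimates a net local-control quantity, which is a defensible question for a nodal boost. DFS and OS count the deaths. However, the plan never says that a net quantity is wanted, independence is untested, and readers will take a control rate as the proportion of patients controlled.

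**Table 1 does not report these deaths directly.** The 31% and 15% come from subtraction and need LRC to count every local-regional failure by that time. If only first failures were scored, the bounds would shrink. Section 4.2 itself reads the prospective trials as showing a "higher incidence of local-regional failures (30-50% at 3 years". It also gives 20% isolated pelvic failures in GOG 125, which suggests that the 30% is not confined to isolated failures. The bounds stand on that reading, although the table does not define LRC.

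**The GOG 125 population is narrower than this trial's.** It had cervical cancer with positive para-aortic nodes, whereas Section 6.1 admits any gynecologic malignancy with involved pelvic or para-aortic nodes. Section 4.4 cites 90% 3-year local-regional control in an endometrial trial. With 10% failure and an assumed 25% competing deaths, the constant-hazard excess is only +1.6 points. This stands: the GOG 125 figures are an illustration, not a forecast.

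**No decision changes, and the present rule errs against the treatment.** The excess is smaller than one SD in all the constant-hazard and early-failure cases, and Section 11.0 sets no threshold or test for these endpoints. Cumulative incidence has its own risk: a recurrence missed before death would count as a competing death and flatter control. Both points stand. They limit the severity and explain why recurrence status at death must be recorded.

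**Conclusion.** The concern holds. As specified, 1-KM for TTLR and TTDR does not estimate the proportion of patients who recur, and it is too high whenever deaths without recurrence precede recurrences. For TTLR, constant hazards and minimum competing deaths put the excess at about 2 to 7 points. It is about 0.5 to 2.6 points if failures come early, and zero if every failure precedes every competing death. These figures take the Table 1 rates as cumulative incidences that count all local-regional failures. For TTDR only the direction is known.

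The consequence is modest: descriptive secondary endpoints in at most 24 patients, with no effect on dose escalation, the MTD, DFS or OS. The change should be made because it is cheap and brings the estimator into line with the objective. The trial's main conclusion does not depend on it.

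**What to change.** In Section 11.0, estimate TTLR and TTDR by cumulative incidence (Aalen-Johansen), with death without the event in question as the competing event. Keep Kaplan-Meier for DFS and OS. The death-censored Kaplan-Meier curve may be shown alongside, labelled as a net estimate, for comparison with published series.

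Record local-regional and distant recurrence status at death. Section 9.1 provides for oncology visits every 3 months, but the follow-up column of its table lists only toxicity assessment, so this item needs to be named.

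The cost is one sentence in Section 11.0, one data item, and slightly more analysis work with standard software. Reported control will look better than under the current rule, and the report should say so.
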